3.13.3.3 Severe Cutaneous Adverse Reaction(s)

Cases of SCARs, including Stevens-Johnson syndrome, and drug reaction with eosinophilia and systemic symptoms (DRESS), which can be life-threatening or fatal, have been reported during treatment with dabrafenib in combination with trametinib. Patients should be advised of the signs and symptoms and monitored closely for skin reactions. If signs and symptoms suggestive of SCARs appear, dabrafenib and trametinib should be permanently discontinued.

3.13.4 Diarrhea

Etiology and attribution. Consider evaluation for an alternative etiology for diarrhea as clinically indicated. These include medications (e.g., stool softeners, laxatives, antacids, etc.), infection by *C. difficile* or *Candida* species, partial bowel obstruction, malabsorption/lactose intolerance, fecal impaction, or diets high in fiber or lactose.

For **Grade ≤ 2 diarrhea**:

- Dietary modifications may include: stop all lactose-containing products and eat small meals. A bananas, rice, apples, toast (BRAT) diet can be helpful.
- Encourage oral hydration according to institutional weight oral hydration guidelines as clinically appropriate.
 - For subjects ≥ 2 years of age, consider administration loperamide ([Table 3-8](#)) with dosing per institutional guidelines or as suggested below. Loperamide is not recommended for children < 2 years of age. Continuation of loperamide is suggested until the subject is diarrhea-free for at least 12 hr.
- If diarrhea resolves to grade ≤ 1 within 72 hr of anti-diarrheal measures or supportive care measures, continue study treatment without interruption or dose reduction.
- If grade 2 diarrhea persists after 72 hr total treatment with loperamide or supportive measures in children <2 years, hold study treatment and consider start of second-line agents (octreotide) as clinically indicated. If diarrhea resolves to grade ≤1 or baseline within 7 days resume study treatment(s) with dose reduction ([Appendix 2](#)). If grade 2 diarrhea does not resolve in ≤ 7 days without study treatment, discontinue protocol therapy.

Table 3-8 Loperamide Dosing for Study Treatment Related Diarrhea

Age	Weight	Initial Dose (start after first loose bowel movement)	Subsequent Doses	Maximum daily dose
>2 to ≤ 12 years	<13 kg	0.5 mg	0.5 mg every 3 hr while awake, every 4 hr during sleep	4 mg/day
	13 to < 20 kg	1 mg	1 mg every 4 hr	6 mg/day
	20 to < 30 kg	2 mg	1 mg every 3 hr while awake, every 4 hr during sleep	8 mg/day
	30 to < 43 kg	2 mg	1 mg every 2 hr while awake, every 4 hr during sleep	12 mg/day
≥ 13 years	≥ 43 kg	4 mg	2 mg every 2 hr	16 mg/day

For Grade 3 to 4 diarrhea:

- Hold study treatment until symptoms resolve to ≤Grade 1 or baseline then may resume study treatment(s) with a dose reduction ([Appendix 2](#)).
- If loperamide has not been initiated, initiate loperamide immediately if age > 2years, using institutional or protocol guidelines for dosing
- For dehydration, use intravenous fluids as appropriate; if severe dehydration, consider administration of octreotide.
- If grade > 2 diarrhea does not resolve in ≤ 7 days without study treatment, discontinue protocol therapy.

3.13.5 Hypertension

The algorithm in [Figure 3-6](#) will be used to grade and manage trametinib and dabrafenib related hypertension. Should initiation of anti-hypertensive therapy be required, single agent therapy (commonly including the calcium channel blockers amlodipine or nifedipine,) should be started and the blood pressure should be monitored at least twice weekly until BP is within the 95th percentile for age, height, and gender per [Section 3.12.3.2](#).

If patient is already on an anti-hypertensive medication at study enrollment, then their anti-hypertensive therapy should be adjusted (by either adjusting the dose of their current anti-hypertensive medication or by adding another anti-hypertensive agent) according to the algorithm in [Section 3.13.5.1](#).

See requirements for Baseline blood pressure measurements in [Section 7.3.4](#).

[figure not shown]
3.13.5.1 Management of Hypertension

- **The upper limit of normal (ULN)** is defined as a BP equal to the 95th percentile for age, height, and gender ([Appendix 7](#)).
- The NCI CTCAE will be utilized to determine the grade of hypertension for reporting purposes.
- Elevated BP measurements should be repeated on the same day to confirm the elevation. Patients with an elevated BP should have BP measurements performed at least twice weekly until BP is ≤ ULN.

- The algorithm below will be used to manage study drug(s) related hypertension.
- Hypertension should be managed with appropriate anti-hypertensive agent(s) as clinically indicated. It is strongly recommended that nephrology or cardiology be consulted in the evaluation and management of hypertension.

Figure 3-6 Algorithm For Management of Study Drug(s)-Related Hypertension

Elevations in BP are based on systolic or diastolic pressures.

† Elevated blood pressure (BP) measurements should be repeated on the same day to confirm the elevation. Patients with elevated BP at any time should have BP measurements performed at least twice weekly until BP is within the ULN.

‡ ULN (Upper Limit of Normal) is a BP equal to the 95th percentile from age, height, and gender-appropriate normal values (Appendix 7)

* If BP >25 mm Hg above ULN for age (verified) or Grade 4 HTN at any time, hold drug. Study drug should also be held for BP ≤ 25 mm Hg above the ULN age for > 14 days or 35 mmHg above baseline for > 14 days. Antihypertensive agents can be used to control hypertension as clinically indicated after study drug is held.

^ Anti-hypertensive therapy should be prescribed as clinically indicated, including the use of multiple anti-hypertensive agents.

* Baseline BP is defined in Section 3.13.3.1.

[figure not shown]
Arm 1 of algorithm:

- If blood pressure (BP) ≤ 95thile for age, height, and gender: continue study drug(s) at the same dose.

Arm 2 of algorithm:

- If BP ≤ 10 mm Hg above the ULN: continue study drug(s) at the same dose and recheck the BP within 72 hours.
 - If the BP is ≤ ULN on recheck, continue study drug(s) at the same dose.
 - If the BP remains above the ULN on recheck, then start/adjust antihypertensive therapy and follow Arm 3 of the algorithm from the point that anti-hypertensive therapy is started/adjusted.

Arm 3 of algorithm:

- If BP is 11 to 25 mm Hg above the ULN on ≥ 2 of 3 measurements or > 35 mmHg above baseline on ≥ 2 of 3 measurements, start/adjust anti-hypertensive therapy and continue study drug(s) at the same dose. Monitor BP at least twice weekly.
 - If the BP returns to \leq ULN within 14 days, continue study drug(s) at the same dose and continue anti-hypertensive therapy.
 - If the BP remains elevated ≥ 25 mm Hg above the ULN or > 35 mm Hg above baseline for more than 14 days after the institution/adjustment of anti-hypertensive therapy, **hold study drug(s)**, monitor BP at least every 3 days, and follow Arm 4 of the algorithm from the point that trametinib is held. The anti-hypertensive therapy should be continued until the BP is less than the ULN.
- If the BP returns to \leq ULN within 14 days, restart study drug (s) at a reduced dose.
- If the BP remains $>$ ULN for more than 14 days, patient must be removed from protocol therapy.
 - If the BP increases to > 25 mm Hg above the ULN despite anti-hypertensive therapy, hold study drug(s), but continue the anti-hypertensive agent(s). Monitor the BP as clinically indicated and follow Arm 4 of the algorithm from the point that study drug(s) is held.
- If the BP is \leq ULN within 14 days, study drug (s) may be restarted at a reduced dose
- If the BP is $>$ ULN for > 14 days, the patient must be removed from protocol therapy (Section 6.3)

Arm 4 of algorithm:

- If BP is > 25 mm Hg above the ULN hold study drug (s), monitor BP, and administer/adjust anti-hypertensive therapy as clinically indicated.
 - If the BP returns to \leq ULN within 14 days, study drug(s) may be restarted at a reduced dose.
 - If the BP is $>$ ULN for >14 days, the patient must be removed from protocol therapy (Section 6.3).

Arm 5 of algorithm:

- If the participant develops Grade 4 hypertension, discontinue study drug(s), monitor BP and administer anti-hypertensive therapy as clinically indicated. The patient is Off Protocol Therapy (Section 6.3).

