V/F	Volume of distribution
XRT	X-Ray Therapy
WBC	White blood cell(s)
WHO	World Health Organization

Amendment 9 (21-Aug-2020)

Amendment Rationale

As of 17-Jul-2020, 139 patients have received study treatment in 5 countries. Parts A, B, C and D have enrolled 50, 41, 18 and 30 patients, respectively. All cohorts have completed enrollment and are now closed. 80 patients in parts A, B, C and D have discontinued study treatment and 13 have enrolled into the CDRB436G2401 Rollover and Follow-up study.

The purpose of this amendment is to add updated RANO criteria specifically for low grade glioma (RANO-LGG; Wen 2017) as the basis for independent review. These more recent RANO-LGG criteria allow for the identification of measurable target lesions in patients with LGG that may not be gadolinium enhancing and are best seen by T2/FLAIR imaging sequences. These updated RANO - LGG criteria will be utilized in supplemental independent RANO response determination for those patients with LGG. Note that the independent response determinations that were originally intended to be applied using the older RANO criteria will be retained for analysis purposes. Also note that the response category of 'minor response' will not be used in this trial.

In addition, the contraception information has been updated following results from a trametinib PK study which showed that no loss of efficacy of combined hormonal contraceptives (norethindrone and ethinyl estradiol) is expected when coadministered with trametinib monotherapy.

Changes in the protocol:

Changes to specific sections of the protocol are shown in the track changes version of the protocol using strikethrough red font for deletions and red underline for insertions:

- List of Abbreviations table: updated to include LGG and RANO
- Removal of named contact details and integrated signature pages in alignment with current Novartis template and standards.
- Section 10.1.1: Updated highly contraceptive methods for female subjects on trametinib monotherapy.
- Appendix 15.5.1: added updated RANO criteria for LGG patients (RANO-LGG) and removed the minor response category in the “Response assessment of target lesions” table as it is not used in this clinical trial.

IRBs/IECs

A copy of this amended protocol will be sent to the Institutional Review Board (IRBs)/Independent Ethics Committee (IECs) and Health Authorities.

The changes described in this amended protocol require IRB/IEC approval prior to implementation.

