The threshold creatinine values in this table were derived from the Schwartz formula for estimating GFR (Schwartz 1985) utilizing child length and stature data published by the Centers for Disease Control and Prevention (CDC).

- Liver function defined as:
 - Bilirubin (sum of conjugated + unconjugated) ≤ 1.5 x ULN for age
 - ALT ≤ 2.5 x ULN; for the purposes of enrollment and toxicity monitoring the ULN for ALT will be 45 U/L.
- Cardiac function defined as:
 - Corrected QT (QTcB) interval <480 msec
 - LVEF \geq LLN by ECHO

8. Able to swallow and retain enterally (PO or nasogastric or gastric tube) administered medication and does not have any clinically significant gastrointestinal abnormalities that may alter absorption such as malabsorption syndrome or major resection of the stomach or bowels.
9. Adequate Blood Pressure Control defined as:
10. Blood pressure \leq the 95th percentile for age, height, and gender) measured as described in [Section 7.3.4](#).
11. **French subjects:** In France, a subject will be eligible for inclusion in this study only if either affiliated to or a beneficiary of a social security category.

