7.3.4 Vital Signs

Vital sign measurements will include systolic and diastolic blood pressure, temperature, respiration rate and pulse rate. Vital signs should be measured after resting for at least 5 minutes in a semi-supine position. Vital signs will be measured more frequently if warranted by clinical condition of the subject. On days where vital signs are measured multiple times, temperature does not need to be repeated unless clinically indicated. Refer to the SPM for details regarding measurement of vital signs. Baseline blood pressure measurement should be performed in triplicate and for all other occasions, measurement should be performed once.

Baseline blood pressure (BP) is defined as the blood pressure obtained at the examination used for study enrollment. This baseline BP should be obtained as follows:

1. Obtain 3 serial blood pressures from the same extremity with the patient in the same position that are separated by at least 5 minutes. Avoid using the lower extremity if possible.
2. Average the systolic blood pressure from the 2nd and 3rd measurements.
3. Average the diastolic blood pressure from the 2nd and 3rd measurements.
4. The baseline BP is the average of the systolic and average of the diastolic measurements.

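### The 14-day hypertension hold in Arm 3 has the opposite sign to the Figure 3-6 footnote, so Arm 3 gives no instruction for most persistent elevations of 1–24 mm Hg above the upper limit of normal

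*Protocol*

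**What the plan says.** Protocol Section 3.13.5 makes Figure 3-6 the working algorithm: it "will be used to grade and manage trametinib and dabrafenib related hypertension". Section 3.13.5.1 sets the ULN at the 95th percentile for age, height and gender. It then gives the rules twice, in the footnotes to the figure and in five written arms.

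**Figure 3-6 footnote.** Drug is held at once for a verified reading more than 25 mm Hg above ULN or for Grade 4 hypertension. The next sentence adds: "Study drug should also be held for BP ≤ 25 mm Hg above the ULN age for > 14 days". The same footnote also holds for 35 mm Hg above baseline lasting more than 14 days.

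**Arm 2.** A child up to 10 mm Hg above ULN who is still above it on recheck starts or adjusts therapy and must "follow Arm 3 of the algorithm from the point that anti-hypertensive therapy is started/adjusted".

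**Arm 3.** This arm is entered at 11 to 25 mm Hg above ULN, or more than 35 above baseline, on at least two of three measurements. Therapy is started or adjusted and drug continues. Three outcomes follow:

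- Return to ULN or below within 14 days: continue at the same dose.
- "If the BP remains elevated ≥ 25 mm Hg above the ULN or > 35 mm Hg above baseline for more than 14 days" after therapy was started or adjusted: hold. After the hold, the child either restarts at a reduced dose (back to ULN within 14 days) or is removed from protocol therapy (still above ULN after more than 14 days).
- A rise to more than 25 mm Hg above ULN despite therapy: hold.

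**Arm 4** also holds for anything more than 25 mm Hg above ULN.

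**The concern.** The two 14-day rules share a clock and a 25 mm Hg cut-off but point in opposite directions. Under the footnote, any elevation up to 25 mm Hg above ULN that lasts beyond 14 days leads to a hold. Under Arm 3, only an elevation of 25 or more does.

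The consequence is not trivial for the individual child. The footnote opens the path to a hold and then to a reduced dose or mandatory removal. A site working from the Arm 3 text alone has no trigger for that path. Two sites could handle the same readings differently, each following a written part of the protocol.

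**Working it through.** No power, sample size or error rate is involved. The check compares two written rules.

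**Which side is in error.** Readings above 25 mm Hg over ULN are held immediately in three places: the footnote, Arm 4 and the last Arm 3 outcome. With the sign as printed, the ULN limb of the Arm 3 14-day rule therefore adds a single value, exactly 25. It also misses nearly all of Arm 3's own 11–25 entry band, and all children arriving from Arm 2 at 1–10 whose pressure stays in that range. With the footnote's sign, the limb covers all of them. The Arm 3 sign is the likely slip.

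**Definitions** (whole mm Hg, elevation lasting more than 14 days on therapy):

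- x = amount above ULN, from 1 to 25.
- d = amount by which baseline lies below ULN. Section 5.2.1.1 requires entry blood pressure at or below the 95th percentile. Section 7.3.4 states: "Baseline blood pressure (BP) is defined as the blood pressure obtained at the examination used for study enrollment". Hence d ≥ 0.
- Amount above baseline = x + d.

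**Rules.**

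- Footnote: hold for every x from 1 to 25.
- Arm 3: hold if x ≥ 25 or x + d > 35.
- Gap (footnote holds, Arm 3 does not): x ≤ 24 and x ≤ 35 − d, that is x ≤ min(24, 35 − d).

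| d (baseline below ULN) | Gap, all x | Gap within the 11–25 band |
|---|---|---|
| 0–11 | 1–24 | 11–24 |
| 12 | 1–23 | 11–23 |
| 15 | 1–20 | 11–20 |
| 20 | 1–15 | 11–15 |
| 25 | 1–10 | none |
| 30 | 1–5 | none |
| 34 | 1 | none |
| 35 or more | none | none |

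**Grid check.** The two rules were compared over 1–40 mm Hg above ULN and 0–60 above baseline, treating the two excesses as free of each other. They disagree exactly where x is 1–24 and the excess over baseline is 0–35: 24 × 36 = 864 combinations. In all 864 the footnote holds and Arm 3 does not. If baseline is at or below ULN, the excess over baseline cannot be less than x. Each x then leaves 36 − x combinations, and the attainable total is 864 − (1 + 2 + … + 24) = 864 − 300 = 564. These are counts of blood pressure values, not of children.

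**Do the later Arm 3 lines fill the gap?** One says that a child still above ULN after more than 14 days must be removed. Its companion line speaks of restarting drug, which presupposes a hold. Read as free-standing, the companion would require a reduced dose for a child back at ULN within 14 days, whereas the first Arm 3 outcome continues the same dose. The removal line would likewise require removal where the footnote requires a hold. Both lines make sense only after a hold, so they do not fill the gap.

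**Exposure.** Amendment 9 reports 139 children treated as of 17 July 2020, of whom "80 patients in parts A, B, C and D have discontinued study treatment". At most 139 − 80 = 59 were still on treatment. This bounds those to whom the rule could still apply; it does not count those affected.

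**The case against.** The best counter-argument is that the section already resolves the matter. Section 3.13.5 makes the figure the governing algorithm, the footnote belongs to the figure, and it is worded as an addition to the immediate hold. No 14-day line in Arm 3 tells a site to continue drug while pressure is still above ULN. A careful reader would hold. This stands, and it is why the point is minor. It does not remove the wrong threshold from the step-by-step text that a site would naturally apply.

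Second, the finding turns on one comparison sign. The flow chart is missing from the copy reviewed, and a sign can be altered when a PDF is converted to text. The indentation that nests the restart and removal lines under the hold is likewise inferred. This also stands as a limit on confidence, so the fix starts by checking the source.

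Third, the full 1–24 range needs a baseline within 11 mm Hg of ULN. The arms apply to systolic or diastolic pressure, so a child escapes the gap if either component meets a hold criterion. The table is therefore an upper bound for each component. That is correct; the gap narrows but does not vanish.

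Fourth, harm is limited. Enrolment is closed, antihypertensive therapy is adjusted, pressure is checked at least twice weekly, specialist consultation is strongly recommended, and a rise above 25 mm Hg over ULN is held at once. All of this is accepted.

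**Conclusion.** The concern holds. As written, Arm 3 and the Figure 3-6 footnote set conflicting 14-day hold thresholds. A child persistently above ULN by up to min(24, 35 − d) mm Hg is held under one and has no instruction under the other. The gap spans 1–24 mm Hg when baseline is within 11 of ULN and closes when baseline is 35 or more below it.

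This rests on the sign being as printed in the sponsor's PDF, on baseline being at or below ULN, and on the restart and removal lines belonging to the hold. The protocol gives no blood pressure distribution, so the number of affected children cannot be estimated. It is a small safety-handling inconsistency in a mandatory dose-hold rule that should be corrected, held with medium confidence. No effect on dose-limiting toxicity counts, dose escalation or endpoints is claimed.

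**What to change.** First check the flow chart and the sign in the source document. If the sign is as printed, reword the Arm 3 criterion so that drug is held when blood pressure remains above ULN but no more than 25 mm Hg above it, or more than 35 mm Hg above baseline, for more than 14 days after therapy was started or adjusted. Under that wording every reading from 1 to 25 mm Hg above ULN leads to a hold at any baseline, as in the footnote.

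Two details should be settled in the same edit. The footnote gives the baseline limb as 35 and Arm 3 as more than 35; use one form. The sponsor should also confirm that the hold, with possible removal, is intended for a child only 1 mm Hg above ULN, since the footnote already implies it.

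The cost is one threshold and a letter to sites, with no change to data collection or analysis. The sponsor must decide whether ethics approval is needed: most of the listed amendments required it before implementation, while Amendment 7 was classed as non-substantial.

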3.13.6 Visual Changes

Episodes of visual changes have been observed in subjects receiving trametinib, and ocular adverse events are known to be related to trametinib. An ophthalmologist should be consulted if changes in vision develop. However, if the visual changes are clearly unrelated to study treatment (e.g., allergic conjunctivitis), then monitor closely as it may be reasonable to defer ophthalmic examination. Special attention should be given to retinal findings (e.g., retinal pigment epithelial detachment (RPED) or retinovascular abnormalities (i.e., branch or central retinal vein occlusions (RVO)). For events of visual changes (regardless of severity) for which

an ophthalmic examination is conducted, a blood sample for PK analysis must be drawn as close as possible to the time of the event ([Section 7.1](#) for PK sample volume).

Guidelines regarding management and dose reduction for visual changes considered to be related to study treatment are provided in [Table 3-9](#).

Table 3-9 Mandatory dose modification and required clinical management for visual changes and/or ophthalmic examination findings

CTCAE v4.03 Grade*	Required adverse event management guidelines	Mandatory dose modification requirements
Grade 1	
 Consult ophthalmologist within 7 days of onset If visual changes are clearly unrelated to study treatment (e.g., allergic conjunctivitis), monitor closely but ophthalmic examination is not required. Report as SAE if RPED or RVO diagnosed 	
 If dilated fundus examination cannot be performed within 7 days of onset, interrupt trametinib until RPED and RVO can be excluded by retina specialist/ophthalmologist. On combination therapy dabrafenib may continue. If RPED and RVO excluded, continue (or restart) trametinib at same dose level If RPED suspected or diagnosed: see RPED dose modification Table 3-10 below If RVO diagnosed: Permanently discontinue trametinib (on combination therapy dabrafenib may continue)
Grade 2 and Grade 3	
 Consult ophthalmologist immediately Report as SAE if RPED or RVO diagnosed 	
 Interrupt trametinib. On combination therapy, dabrafenib may be continued at the same dose. If RPED and RVO excluded, restart trametinib at same dose level If RPED diagnosed, see RPED dose modification Table 3-10 below If RVO diagnosed: Permanently discontinue trametinib (on combination therapy dabrafenib may continue) Permanently discontinue dabrafenib for \geq Grade 2 uveitis (including iritis and iridocyclitis) of > 6 weeks duration.
Grade 4	
 Consult ophthalmologist immediately Report as SAE if RPED or RVO diagnosed 	
 Interrupt trametinib. On combination therapy, dabrafenib may be continued at the same dose. If RPED and RVO excluded, may consider restarting trametinib at same or reduced dose If RPED or RVO diagnosed, permanently discontinue trametinib (on combination therapy dabrafenib may continue).

* Refers to NCI-CTCAE v4.03 'Eye disorders – Other, specify

Table 3-10 Mandatory dose modification and required clinical management for retinal pigment epithelial detachments (RPED)

CTCAE v4.03 Grade*	Required adverse event management guidelines	Mandatory dose modification requirements
Grade 1 RPED (Asymptomatic; clinical or diagnostic observations only)	
 If RPED worsens follow instructions below. 	Continue treatment with retinal evaluation monthly until resolution.

Grade 2-3 RPED (Symptomatic with mild to moderate decrease in visual acuity; limiting instrumental ADL)	
 • Retinal evaluation monthly. 	
 • Interrupt trametinib (on combination therapy dabrafenib may continue) 
If improved to \leq Grade 1, restart trametinib at lower dose (Appendix 2, dose reduction column)

---	---	---

* Refers to CTCAE Version 4.0 'Retinopathy'

